Appendix D. Analysis of Continuous Endpoints using Mixed Effect Model Repeat Measurement (MMRM)

The repeated measure analysis will be conducted using mixed model including observed data at all visits. For the MMRM analysis, data collected after premature discontinuation of study drug will be excluded. The mixed model includes the categorical fixed effects of treatment, visit and treatment-by-visit interaction, main stratification factors at randomization and the continuous fixed covariates of baseline measurement. An unstructured variance covariance matrix will be used. The parameter estimations are based on the assumption of data being missing at random and using the method of restricted maximum likelihood (REML).

The MMRM is implemented using the SAS procedure PROC MIXED. The LSMEANS statement provides the least-squares means and corresponding 95% CIs for each treatment group at each visit, as well as the least-squares means, corresponding 95% CIs and p-values for treatment comparisons at each visit. The SAS code example is as follows:

```
proc mixed data=CData;  
  class TRTP AVISIT STRATA USUBJID;  
  model CHG = TRTP AVISIT BASE STRATA TRTP*AVISIT / DDFM=kr htype = 3;  
  repeated AVISIT / subject = USUBJID type=un;  
  lsmeans TRTP*AVISIT/ cl diff;  
  ods output lsmeans=lsmean_output;  
  
run;
```

Note: The input dataset is per subject per visit. USUBJID is the unique subject number, TRTP denotes the treatment group, STRATA denotes the strata, and AVISIT denotes the visit. CHG denotes the change from baseline value and BASE denotes the baseline value.

Appendix E. Tipping Point Analysis

Tipping Point Analysis for binary endpoint ASAS40 (and ASAS 20)

To assess the robustness of the primary analysis using NRI data handling, tipping point analysis is conducted on the primary endpoint ASAS40. The analysis is conducted using As Observed data handling.

Let M_1 be the number of subjects missing ASAS40 status in the placebo group, and let M_2 be the number of subjects missing ASAS40 status in the upadacitinib group. Let X_1 be the number of subjects imputed as ASAS40 responders out of the M_1 subjects with missing ASAS40 status in the placebo group – the rest are imputed as non-responders. X_1 can take values from 0 to M_1 . Similarly define X_2 . Given each pair of (X_1, X_2) , we can obtain the p-value for the treatment comparison of upadacitinib versus placebo using the combined observed data and imputed data for each treatment group. If one pair of parameters are found to just reverse the study conclusion, in terms of p-value larger than 0.05 (the original p-value < 0.05), then these parameters are called the tipping point.

Tipping Point Analysis for Continuous Endpoints

To assess the impact of potential departures from the missing-at-random assumption, tipping point analyses are conducted as a sensitivity check for change from baseline in ranked secondary endpoints at the primary time point. The tipping point analyses are two-dimensional, i.e., assumptions about the missing outcomes on the upadacitinib treatment group and the placebo group are allowed to vary independently. In addition, the focus is on scenarios where missing outcomes on upadacitinib are worse than the imputed values on upadacitinib, while missing outcomes on placebo are better than the imputed values on placebo. Missing values are first imputed via multiple imputation (MI) under MAR, and then a shift parameter is applied to the imputed values (a different shift parameter may be specified for each treatment group). (The MI imputation is performed upon AO data). This is implemented by PROC MI using the MNAR statement. For a given pair of shift parameters, the SAS code example is as follows:

```
PROC MI DATA=DATA WIDE OUT=OUTMI NIMPUTE=5 SEED=12345
  MINMAXITER=1000;
  CLASS TRTP COVCAT;
  MONOTONE;
  VAR TRTP COVCON COVCAT WEEK_2 WEEK_4 WEEK_8 WEEK_12;
  MONOTONE REG( WEEK_2 = TRTP COVCON COVCAT );
  MONOTONE REG( WEEK_4 = TRTP WEEK_2 COVCON COVCAT );
  MONOTONE REG( WEEK_8 = TRTP WEEK_2 WEEK_4 COVCON COVCAT );
  MONOTONE REG( WEEK_12 = TRTP WEEK_2 WEEK_4 WEEK_8 COVCON COVCAT );
  MNAR ADJUST (WEEK_12 / SHIFT=&SJ1 ADJUSTOBS=(TRTP='PLACEBO'));
  MNAR ADJUST (WEEK_12 / SHIFT=&SJ2 ADJUSTOBS=(TRTP='UPA 15MG'));
RUN;
```

Note: The input dataset is the same as that used for MI analysis. The macro variables SJ1 and SJ2 denote the shift parameters for the placebo group and the upadacitinib group respectively.

In cases where the shifted values are smaller than the minimum or larger than maximum value of the endpoints, (i.e., out of range), the minimum or maximum value is used in further analysis steps. For each pair of shift parameters, the same analysis as the primary MI analysis is then conducted to obtain the p-values for the upadacitinib treatment group versus the placebo group. If one pair of shift parameters are found to just reverse the study conclusion, in terms of p-value larger than 0.05 (the original p-value < 0.05), then the shift parameters are identified as the tipping point. The results for a grid of shift parameter combinations are provided in tabular format.

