In order to minimize missing data for efficacy and safety assessments, subjects who prematurely discontinue study drug treatment should complete a PD visit as soon as possible, preferably within 2 weeks. Afterwards, subjects should continue to be followed for all regularly scheduled visits as outlined in [Appendix E](#) and adhere to all study procedures except for dispensing study drug, PK sample collection, blood sample collection for optional exploratory research and validation studies, and x-rays. (New x-rays are dependent on the time of discontinuation; refer to Section 5.3.1.1 for details.) In addition, all future efficacy-driven discontinuation criteria no longer apply (ASAS 20 response). Subjects should be advised on the continued scientific importance of their data even if they discontinue treatment with study drug early.

If a subject prematurely discontinues study participation (withdrawal of informed consent), the procedures outlined for the PD visit should be completed as soon as possible, preferably within 2 weeks. In addition, a 30-day follow-up visit (or phone call if a visit is not possible) should occur to determine the status of any ongoing AEs/SAEs or the occurrence of any new AEs/SAEs. Subjects who discontinue the study prematurely after randomization will not be replaced.

All attempts must be made to determine the date of the last study drug dose and the primary reason for discontinuation of study drug or study participation. The information

will be recorded on the appropriate eCRF page. However, these procedures should not interfere with the initiation of any new treatments or therapeutic modalities that the Investigator feels are necessary to treat the subject's condition. Following discontinuation of study drug, the subject will be treated in accordance with the Investigator's best clinical judgment, irrespective of whether the subject decides to continue participation in the study.

Lost to Follow-Up

For subjects to be considered lost to follow-up, reasonable attempts must be made to obtain information on the final status of the subject. At a minimum, two phone calls must be made, and one certified letter must be sent and documented in the subject's source documentation.

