9.1.2 Handling for Missing Data and Intercurrent Event

Non-Responder Imputation (NRI) Approach

The NRI approach will handle data for binary variables as follows.

- Subjects who prematurely discontinue from study drug will be considered as non-responders for all subsequent visits after discontinuation.

- In addition, any subject with any missing value for binary variables at a specific visit will be treated as non-responder for that visit.

The NRI data handling will be used for the primary estimand (refer to Section 9.2.1) for binary variables.

As Observed (AO)

The AO data handling will not impute values for missing evaluations, and thus a subject who does not have an evaluation on a scheduled visit will be excluded from the AO analysis for that visit. Regardless of premature discontinuation of study drug, all observed data will be used in the analysis. The AO data handling will be used to facilitate the supplementary analysis for both binary and continuous variables (refer to Section 9.2.2 and Section 9.2.3 where the corresponding supplementary estimand for the primary and ranked secondary endpoints is described respectively).

Mixed Effect Model Repeat Measurement (MMRM)

The repeated measure analysis will be conducted using mixed model including observed data at all visits. For the MMRM analysis, data collected after premature discontinuation of study drug will be excluded. The mixed model includes the categorical fixed effects of treatment, visit and treatment-by-visit interaction, main stratification factors at randomization and the continuous fixed covariates of baseline measurement. An unstructured variance covariance matrix will be used. The parameter estimations are based on the assumption of data being missing at random and using the method of restricted maximum likelihood (REML). MMRM will be used for the primary estimand of continuous variables (refer to Section 9.2.3).

Longitudinal Analysis for Long-Term Efficacy: MMRM and Generalized Linear Mixed Model (GLMM)

The repeated measure analysis will be conducted using mixed model including AO measurements at all visits. MMRM will be used for continuous endpoints and GLMM will be used for binary endpoints. The mixed models will include the categorical fixed

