For continuous key secondary efficacy endpoints, the estimand is the difference in mean change from baseline at Week 14 under the assumption that patients with missing data including those due to premature discontinuation of study drug can have their measurements at Week 14 predicted by their observed data and the observed data for other patients for their respective assessments during follow-up. The comparison is Upadacitinib 15 MG QD vs placebo for patients randomized and treated with at least one dose of study drug.

For the primary estimand of the continuous key secondary efficacy endpoints, statistical inference will be conducted using the MMRM model and the associated data handling as described in Section 9.1.2, with the main stratification factor of hsCRP level (\leq ULN vs. $>$ ULN). The LS mean and 95% CI will be reported for each randomized treatment group; the LS mean treatment difference and associated 95% CI and p-value will be reported comparing Upadacitinib with the placebo group.

The supplementary analysis for secondary continuous variables will be conducted on AO cases using the analysis of covariance (ANCOVA) model with treatment and the stratification factor of hsCRP (\leq ULN vs. $>$ ULN) as the fixed factor and the corresponding baseline value as the covariate. The corresponding estimand is the difference in the mean change from baseline in the efficacy endpoints at Week 14 regardless of premature discontinuation of study drug. The comparison will be the Upadacitinib 15 MG QD vs placebo for patients randomized and treated with at least one dose of study drug and have the efficacy measurement available at Week 14. To explore various missing data assumptions including missing not at random (MNAR), the tipping point analysis will also be conducted using multiple imputation (MI) as additional supplementary analysis. Details of the tipping point analysis are outlined in Appendix E.

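### The continuous tipping-point analysis imputes from as-observed data, so it does not test the MMRM's missing-at-random assumption for subjects who stop drug but have a Week 14 value

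*SAP*

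**What the plan says.** **Primary analysis.** For the continuous endpoints, SAP 9.1.2 states that "MMRM will be used for the primary estimand of continuous variables". Appendix D gives its data rule, "For the MMRM analysis, data collected after premature discontinuation of study drug will be excluded", and its assumption, "The parameter estimations are based on the assumption of data being missing at random". The estimand in SAP 9.2.3 is worded to match: "patients with missing data including those due to premature discontinuation of study drug can have their measurements at Week 14 predicted by their observed data". Data from the other patients also feed that prediction.

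**AO handling.** SAP 9.1.2 imputes nothing and uses every observed value, whether or not the subject is still on drug.

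**Tipping point.** SAP Appendix E says the continuous version examines departures from missing-at-random for the ranked secondaries at the primary time point. It adds that "The MI imputation is performed upon AO data" and applies the shift to imputed values only. Then "the same analysis as the primary MI analysis is then conducted to obtain the p-values", and the tipping point is the shift pair that just overturns the study conclusion. The example code lists Weeks 2, 4, 8 and 12 and shifts Week 12.

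**Follow-up.** Protocol 5.4.1 says of those who stop drug that "subjects should continue to be followed for all regularly scheduled visits". Protocol 5.1 also allows complete withdrawal at any time.

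**The concern.** A tipping-point analysis informs about a result only if it varies the values which that result treats as missing. The MMRM treats every value after drug discontinuation as missing and predicts it. The tipping-point imputation treats those same values as data wherever they were collected, and the protocol asks for them to be collected. So the group for whom the MMRM leans on its assumption, despite an off-drug Week 14 value being available, is left out of the stress test.

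At stake is how the robustness table is read. With fewer values shifted, the reported tipping shift will generally be larger, or no tipping point will appear. A reader could take as robustness of the MMRM result what is really a consequence of data handling. In addition, the p-value step cannot be programmed from the SAP, because it refers to an analysis that is not defined.

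**Working it through.** **1. The two rules side by side**

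| Subject | MMRM (SAP 9.1.2, Appendix D) | Tipping point (Appendix E on AO data) |
|---|---|---|
| On drug, Week 14 observed | used | used, not shifted |
| On drug, Week 14 missing | missing, predicted | imputed and shifted |
| Stopped drug, no Week 14 value | missing, predicted | imputed and shifted |
| Stopped drug, Week 14 observed | excluded, predicted | used, **not shifted** |

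Only the last row differs. The imputation model in the third row is also fitted to data that include off-drug values.

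**2. Which endpoints are most affected (SAP 5.2)**

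| Ranked endpoint | Week 14 window opens | Table |
|---|---|---|
| ASDAS, BASFI | Day 93 | 1 |
| ASAS HI | Day 79 | 3 |
| AS QoL, MASES | Day 79 | 4 |
| WPAI, BASMI | Day 2 | 5 |
| MRI SPARCC (spine) | Day 4 | 6 |

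In Tables 5 and 6, Week 14 is the only post-baseline window in Period 1. A premature-discontinuation assessment, or an MRI rescheduled within 14 days of that visit (Protocol 5.3.1.1), can therefore count as the AO Week 14 value. Few discontinuers may be left to shift. Spine SPARCC is listed second among the key secondaries. For the other endpoints, subjects who leave the study before the window opens stay missing and are shifted.

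**3. Size, as an illustration**

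The plan states no figure for this analysis. I borrow 85 per arm and the 10% dropout rate from Protocol 8.2. (That sample size reproduces: 75 per arm for 90% power at 20% versus 46% with continuity correction; 75/0.9 = 83.3, so 84 per arm and 168 in total, against 170.)

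Assumptions not in the documents: the 10% is read as drug stopping (*d*); *f* is the share of stoppers with an observed Week 14 value; the unshifted z is 3.0 in both datasets; equal and opposite shifts are applied in the two arms; the limit that Appendix E sets on out-of-range values is ignored.

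- Standard error in SD units: √(2/85) = 0.1534.
- Movement needed to bring z from 3.0 to 1.96: 1.04 × 0.1534 = 0.1595 SD.
- A shift *s* in each arm moves the difference by 2·*d*·(1−*f*)·*s*, so *s* = 0.1595 / [2·*d*·(1−*f*)].

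With MMRM data, 8.5 subjects per arm are shifted and *s* = 0.1595/0.20 = 0.80 SD. On AO data with *d* = 0.10:

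| *f* | Shifted per arm, 8.5(1−*f*) | Tipping shift (SD) |
|---|---|---|
| 0 | 8.5 | 0.80 |
| 0.5 | 4.25 | 1.60 |
| 0.75 | 2.1 | 3.19 |
| 0.9 | 0.85 | 7.98 |
| 1 | 0 | none exists |

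At *f* = 0.5, the AO shift is 3.19 SD if 5% stop (1.60 on MMRM data) and 1.06 SD if 15% stop (0.53 on MMRM data).

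A simulation on a 0 to 10 scale agrees in direction. It assumed 85 per arm, 10% stopping, a difference of −1.0, SD 2.2, a shift in the upadacitinib arm only, and significance at zero shift. The median tipping shift was about 4 points with all discontinuers imputed, against 5.4, 7.0 and 10.4 points on AO data when 30%, 50% and 70% of them had a Week 14 value. When shifted values were held within the scale, as Appendix E requires, 13 to 15% of trials had no tipping point with all discontinuers imputed, against 30%, 64% and 74% on AO data.

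**4. The analysis after the shift**

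The primary analysis is MMRM and the AO supplementary analysis is ANCOVA. In the body of the SAP (9.2.3), multiple imputation appears only as the tipping point itself, so the analysis that Appendix E repeats does not exist elsewhere. The code's last visit is Week 12, although the endpoints are at Week 14.

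**The case against.** **AO may have been intended.** SAP 9.2.3 introduces the continuous tipping point straight after the AO ANCOVA, in the same paragraph, and calls it additional supplementary analysis. Appendix E states the AO input openly. For the binary endpoint it names the NRI primary analysis as its target; for continuous endpoints it names neither the MMRM nor the primary analysis. Read as support for the AO estimand, the data handling is coherent. This fits the placement but not the stated purpose. For Period 1, the SAP attaches missing-at-random to the MMRM, and the AO ANCOVA states no such assumption. The conclusion to be overturned for these endpoints also comes from the MMRM. If AO was the target, the SAP should say so.

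**Off-drug outcomes are not ignored.** The AO ANCOVA uses them and shows whether the finding survives them. That stands, but it answers a different question from the MMRM estimand.

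**The figures are soft.** This stands in full. The 10% is a dropout rate; if it means leaving the study, those subjects are missing under both rules and the gap shrinks. Retention, effect, SD and z are assumptions. Nor must the AO shift be larger in every case: if off-drug upadacitinib values lose their effect, the AO comparison starts from a smaller difference, the gap narrows, and a given trial can tip sooner.

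**It is supplementary.** No primary estimate, ranked p-value or multiplicity step depends on it. True, and it limits the seriousness.

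**Conclusion.** The point holds in a limited form. The continuous tipping-point analysis leaves the MMRM's missing-at-random assumption unstressed for subjects who stop drug and have an observed Week 14 value, and its post-shift analysis is undefined. Both follow from the text and need no assumed numbers.

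A reader might infer that the assumption is never tested for anyone who stops drug, or that the continuous secondaries have no sensitivity analysis at all. The documents do not support either reading: discontinuers without a Week 14 value are imputed and shifted. The stronger reading comes close only for WPAI, BASMI and MRI SPARCC, because of their wide Week 14 windows.

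The expected direction is a larger tipping shift or none found. The amount depends on how many discontinuers have a Week 14 value and on their off-drug outcomes. The factor of two at *f* = 0.5 illustrates the mechanism and is not an estimate for this trial. The correction is worth making because robustness statements for the ranked continuous secondaries would rest on this table.

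**What to change.** In SAP Appendix E:

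1. Set values after premature drug discontinuation to missing before imputation, as the MMRM does.
2. Extend the imputation to Week 14 and apply the shift there.
3. Replace the undefined analysis with a named one, for example a Week 14 ANCOVA with treatment, hsCRP stratum and baseline, combined by Rubin's rules.
4. Check that the zero-shift cell is close to the MMRM result, and explain any discrepancy.
5. Keep the AO version as a second table, labelled as supporting the AO estimand.

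**Cost.** A wording change and one more programmed dataset, with no new data collection. The reported tipping points may be less favourable. SAP section 11.0 puts the Week 14 lock in February 2019, so for Period 1 the new table should be labelled as an additional analysis specified after that lock.

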4.2 Overall Study Design and Plan

This is a Phase 2/3, multicenter study that includes two periods. Period 1 is the 14-week randomized, double-blind, parallel-group, placebo-controlled period designed to compare the safety and efficacy of Upadacitinib 15 mg QD versus placebo for the treatment of signs and symptoms of subjects with active AS who have had an inadequate response to at least two NSAIDs over an at least 4-week period in total at maximum recommended or tolerated doses or intolerance to or a contraindication for NSAIDs as defined by the Investigator, and who are bDMARDs-naïve. Period 2 is an open label long-term extension to evaluate the long-term safety, tolerability, and efficacy of Upadacitinib 15 mg QD in subjects with AS who have completed Period 1.

The study is designed to enroll approximately 170 subjects at approximately 110 study centers worldwide to meet scientific and regulatory objectives without enrolling an undue number of subjects in alignment with ethical considerations.

The study duration includes a 35-day screening period; a 14-week randomized, double-blind, placebo-controlled treatment period (Period 1); a 90-week open label extension period (Period 2); and a 30-day follow-up visit. After Week 104, subjects in France, Germany, Belgium, Finland, and Netherlands will be evaluated for safety and tolerability of upadacitinib every 12 weeks until the end of the study.

X-rays of the pelvis will be performed within the 35-day screening period to evaluate the SI joints to confirm the fulfillment of the modified New York Criteria for AS. X-rays of the spine will also be performed within the 35-day screening period to assess for total spinal ankylosis; subjects with total spinal ankylosis are not eligible for this study. The x-rays of the spine and pelvis will not be required during the Screening Period if the subject had a previous anteroposterior (AP) pelvis x-ray and lateral spine x-rays within

90 days of the Screening Period, provided that the x-rays are confirmed to be adequate for the required evaluations and are deemed acceptable by the central imaging vendor.

Subjects who meet eligibility criteria will be randomized in a 1:1 ratio to one of two treatment groups:

- Group 1: Upadacitinib 15 mg QD, N = 85 (Day 1 to Week 14) → Upadacitinib 15 mg QD (Week 14 and thereafter)
- Group 2: Placebo, N = 85 (Day 1 to Week 14) → Upadacitinib 15 mg QD (Week 14 and thereafter)

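### The continuous tipping-point analysis is specified only through example code with 5 imputations, so the reported boundary carries avoidable, modest, seed-dependent Monte Carlo error (minor)

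*SAP*

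**What the plan says.** SAP Appendix E covers the continuous ranked secondary endpoints: "tipping point analyses are conducted as a sensitivity check for change from baseline in ranked secondary endpoints at the primary time point". Missing values are imputed under missing at random, a separate shift is added in each arm, and the treatment comparison is repeated for each pair of shifts. On the input data it says "The MI imputation is performed upon AO data".

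The number of imputations appears once, in code introduced by "For a given pair of shift parameters, the SAS code example is as follows". The code line reads "NIMPUTE=5 SEED=12345". Only the two shift macro variables change between cells.

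The decision rule is a fixed threshold: "in terms of p-value larger than 0.05 (the original p-value < 0.05), then the shift parameters are identified as the tipping point". For output, "The results for a grid of shift parameter combinations are provided in tabular format". Neither document gives another number of imputations, a grid step or range, or a Monte Carlo error check. Shifted values outside the scale are set to its minimum or maximum.

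**The concern.** The quantity reported is the place where p crosses 0.05, so it is read from the cells most exposed to imputation noise. With few imputations the pooled p-value at such a cell depends on which draws the seed happened to produce.

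SAP Section 9.2.3 names this analysis as the one that explores missing-not-at-random departures for the continuous secondary endpoints. The MMRM assumes missing at random, and the supplementary ANCOVA uses observed cases only. If the boundary depends on an arbitrary seed, the stated margin of robustness can be somewhat too wide or too narrow, in an unknown direction.

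**Working it through.** **The plan's own figure.** The documents give no Monte Carlo or tipping-point figure to reproduce. The one input that can be checked is the arm size. For 20% against 46%, two-sided 0.05 and 90% power with continuity correction, 75 evaluable per arm are needed; 75/0.90 is about 84 per arm, 168 in total, close to the planned 170. So 85 per arm is used below.

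**Inputs from the documents.** M = 5 and one seed (SAP Appendix E); cut at 0.05 (SAP Appendix E); 85 per arm (SAP Section 4.2); 10% dropout (SAP Section 4.3), the only missingness figure given.

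**Assumptions.** Missingness at Week 14 of 5%, 10% or 20% per arm; standardised effect 0.5–0.75; correlation 0.6–0.7; equal and opposite shifts in the two arms; no truncation. Appendix E refers to a primary MI analysis that the SAP does not define elsewhere. ANCOVA pooled by Rubin's rules with Barnard-Rubin degrees of freedom was used.

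**Step 1: simulation.** The observed data were held fixed, the shift was set so that the many-imputation p is 0.050, and only the imputation draws varied. Central 95% of p:

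| Missing per arm | M = 5 | M = 20 | M = 100 | M = 500 |
|---|---|---|---|---|
| 5% | 0.033–0.075 | – | – | – |
| 10% | about 0.025–0.10 | 0.034–0.068 | 0.043–0.058 | 0.047–0.053 |
| 20% | 0.017–0.16 | 0.029–0.087 | 0.040–0.064 | 0.045–0.055 |

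The predictors matter. At 10% missing and M = 5, one earlier visit gives 0.029–0.089 and baseline alone gives 0.024–0.101. At 5% missing, baseline alone gives 0.029–0.084. The baseline-only case applies to MRI spine SPARCC, BASMI and WPAI, which have no post-baseline window before Week 14 in Period 1 (SAP Tables 5 and 6).

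**Step 2: formula check.** The Monte Carlo SD of the test statistic is about √(FMI/M), where FMI is the fraction of missing information.

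- FMI 0.125 (20% missing, several visits), M = 5: √(0.125/5) = 0.158; 1.96 ± 1.96 × 0.158 = 1.65 to 2.27; p = 0.099 to 0.023. Simulated in that setting: 0.018–0.116.
- FMI 0.125, M = 100: √(0.125/100) = 0.035; z = 1.89 to 2.03; p = 0.059 to 0.042. Simulated: 0.040–0.058.
- FMI about 0.05 (10% missing), M = 5: √(0.05/5) = 0.10; z = 1.76 to 2.16; p = 0.078 to 0.031.

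The formula treats the pooled standard error as known, so it is too narrow at M = 5, where the between-imputation variance rests on five values. It supports the order of magnitude and the gain from raising M.

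**Step 3: on the shift scale.** At 10% missing and M = 5 the tipping shift has SD about 0.07–0.10 outcome SD around roughly 2–2.7 SD. The 95% half-width is 1.96 × 0.07 = 0.14 to 1.96 × 0.10 = 0.20 SD, that is 0.14/2.7 = 5% to 0.20/2.0 = 10% of the shift. Going from 5 to 100 imputations divides the SD by √(100/5) = 4.5, to about 0.02. At 20% missing the tipping shift is smaller (0.92–1.55 SD) with SD 0.06–0.09, so the error is relatively larger.

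**Step 4: over a grid.** For shifts from 0 to 3 SD in each arm at 10% missing, the chance that at least one cell falls on the other side of 0.05 from the many-imputation answer is:

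| Grid step | M = 5 | M = 100 |
|---|---|---|
| 0.25 SD | 76–92% | 53–67% |
| 0.5 SD | 63–64% | 25–29% |
| 1 SD | 36–38% | 15–19% |

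At step 0.25 SD there are 13 × 13 = 169 cells. The mean number misplaced falls from about 6 (3.6%) to about 1–2.

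**The case against.** Several points on the other side stand.

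- **The seed is already fixed.** A reader might infer that cells flip in and out independently. The code does not support that: one seed serves every cell and only the shifts change, so all cells share the same draws and the boundary moves as one. What remains is a single common displacement that another seed would change.
- **p at a 0.05 cell is the worst case.** The output is a shift, and on that scale the error is modest. Cells far from 0.05 do not change.
- **Missingness may be lower.** As Observed data keep values after drug discontinuation (SAP Section 9.1.2), and the protocol asks for continued follow-up (Section 5.4.1). At 5% the p range is clearly narrower than at 10%.
- **Truncation is not modelled.** Appendix E clips out-of-range values, which limits how far a shift can act. On a bounded scale with little missing data there may be no tipping point at all.
- **The code is a template.** It is labelled an example and stops at Week 12, although the endpoints are at Week 14. A reader might infer that 5 imputations were certainly used; the documents do not establish that. But they state no other number.
- **100 is not a magic number.** M = 20 already helps, and M = 100 still misplaces some cell in over half of fine grids.

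In the other direction, MASES is analysed only in subjects with baseline enthesitis and overall work impairment only in the employed. Those endpoints therefore have fewer than 85 per arm, and the ranges may differ.

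**Conclusion.** The point holds as a minor precision issue in a supplementary analysis. The plan pairs a hard p cut with the smallest specification of M it could be read to have, and at that cut M = 5 leaves p uncertain by roughly a factor of two either way at 10% missing, less at 5%. The missing rates, effect size, correlation, pooled analysis and lack of truncation are assumptions.

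A reader might infer that the robustness conclusions are unreliable, or that the ranked tests are affected. The documents do not support either. A strongly robust result would still read as robust, and only a result with a small tipping shift could be described differently. The primary CMH test, the MMRM tests and the multiplicity sequence use no imputation draws. The binary tipping-point analysis enumerates every responder count and has no random element.

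**What to change.** State in the text of Appendix E, as well as in the code, that every grid cell uses at least 100 imputations. Keep the single seed already there. For cells near 0.05, report the Monte Carlo error of the p-value, and use about 500 imputations if that error could change the side of the cut.

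SAP Section 11 says the Week 14 database lock was completed in February 2019. For these endpoints the step is therefore to report the number of imputations actually used and, if it was 5, to rerun the grid. No new data are needed; the cost is one number in the code and a little computing time.
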